10.1.4.1	Global Clinical Assessment (GCA).....	24
10.1.4.2	Activities of daily living (ADL) rating / Karnofsky performance status scale	24
10.1.4.3	Quality of life scale / EORTC QLQ-C30	24
10.1.4.4	Pain scale	24
10.1.4.5	Eastern Cooperative Oncology Group (ECOG) performance status	24
10.2	Statistical Analysis Methods	25
11	SAFETY ANALYSES.....	25
11.1	Safety Outcomes	25
11.1.1	Subject disposition	25
11.1.2	AEs.....	26
11.1.3	Clinical laboratory evaluations	27
11.1.4	Vital signs and weight	27
11.1.5	12-Lead electrocardiogram (ECG).....	28
11.1.6	Physical examination	28
11.1.7	Murine antigens skin test	28
11.1.8	Murine leukemia virus	28
12	MISCELLANEOUS DATA COLLECTION.....	28
12.1	Subject Progress	28
13	STATEMENT OF COMPLIANCE	28
14	SOFTWARE	28

15 REFERENCES	29
16 APPENDICES	30
16.1 Listings	30
16.2 Tables	32
16.3 Figures	34

List of Abbreviations

ADL	Activities of daily living
AE	Adverse event
ALT	Alanine aminotransferase
AST	Aspartate aminotransferase
BUN	Blood urea nitrogen
CA	Cancer antigen
CEA	Carcinoembryonic antigen
CI	Confidence interval
CRA	Clinical Research Associate
CRF	Case report form
CSR	Clinical study report
CT	Computerized tomography
CTCAE	Common terminology criteria for adverse events
DM	Data management
ECG	Electrocardiogram
ECOG	Eastern Cooperative Oncology Group
EORTC	European Organisation for Research and Treatment in Cancer
EOS	End of study
ESR	Erythrocyte sedimentation rate
GCA	Global clinical assessment
GGT	Gamma glutamyl-transpeptidase
ICF	Informed consent form
Ig	Immunoglobulin
IL	Interleukin
INR	International normalized ratio
KPS	Karnofsky Performance Status
LLT	Lowest level term
MedDRA®	Medical Dictionary for Regulatory Activities
MRI	Magnetic resonance imaging
NK	Natural killer
PA	Posteroanterior
PCR	Polymerase chain reaction
PET-CT	Positron emission tomography - computed tomography

PFS	Progression-free survival
PI	Principal Investigator
PT	Preferred term
PT	Prothrombin time
PTT	Partial thromboplastin time
QLQ-C30	Quality of life questionnaire - C30
RENCA	Renal adenocarcinoma
SAS®	Statistical Analysis System
SAP	Statistical analysis plan
SOC	System organ class
TEAE	Treatment-emergent adverse event
TNF	Tumor necrosis factor
T ₀	Time of origin
VAS	Visual analog scale
VSI	Vital Systems, Inc.
WHO [®] DD	World Health Organization drug dictionary

List of Definitions

Concomitant Medication	Medication taken up to \leq 30 days before the first implantation up to 90 days after the last implantation
End of Study	When all patients have died or have been lost to follow-up, whichever occurs first
Enrolled Patients	Eligible patients who have signed an Informed Consent Form (ICF)
Sponsor	The Rogosin Institute
Time of origin (T_0)	Date of the first scan showing disease progression after completion of prior treatment. Scan must be prior to first implant. Used for mortality analyses only.
Treated Population	Patients who received at least one implant
Treatment-Emergent Adverse Event (TEAE)	An adverse event which occurred during or after the first implantation and up to 120 days after the last implantation

1 ADMINISTRATIVE STRUCTURE

This study is being conducted under the sponsorship of The Rogosin Institute (“the Sponsor”). The clinical monitoring, data management and statistical analyses of safety and efficacy are being performed under contract with Vital Systems, Inc. (VSI), in collaboration with the Sponsor.

This SAP supersedes any statistical considerations identified in the study protocol. Any differences between this statistical analysis plan and the study protocol will be presented and explained in the CSR.

1.1 Data Quality Assurance

The Investigator and site staff will be responsible for the validity of data collected at the clinical site and will be subject to the various monitoring procedures put in place for the study. Study monitoring will be done by a Clinical Research Associate (CRA) to ensure that:

- the rights and well-being of human subjects are protected
- trial data are accurate, complete, and verifiable with source data
- the trial is conducted in compliance with the protocol, Good Clinical Practices, and the applicable regulatory requirements.

The Principal Investigator and VSI will agree to allow the study monitor (Clinical Research Associate; CRA) to inspect all Case Report Forms (CRFs) and corresponding source documents, e.g., original medical records and other patient-related data sources, laboratory raw data, and records of surgical implantation as requested, and to provide adequate time and space for monitoring visits.

The study monitor will query the site on missing or spurious data and these will be resolved in a timely manner. A monitoring log will be maintained recording each visit of the study monitor, the reason for the visit, and the monitor’s signature. Activities performed by the study monitor will be recorded in a monitoring report to be reviewed by the Sponsor.

Sources of data are detailed in the Data Management (DM) Plan; these include CRFs, laboratory and imaging reports, and additional laboratory data. CRFs and laboratory reports will be transferred to DM via traceable courier with a transmission log of the documents sent. DM personnel will verify receipt of every page expected and will review the CRFs for legibility, completeness and internal consistency. A comprehensive page inventory will also be reviewed and verified with the site prior to database lock to confirm receipt of all available pages for all study subjects.

Data will be independently entered by two operators into a validated computer system. Any discrepancies between the entries will be resolved by the Data Manager or queried to the site for clarification if necessary. Computerized algorithms will be used to check for incomplete, inconsistent or illogical values and any issues will be investigated via queries to the site. Data points that trigger edit check failures (e.g. values which are outside of the algorithms) but which are subsequently confirmed to be valid values will be suppressed in the edit check system and documented by DM as known data anomalies.

All data will be compiled into Statistical Analysis System (SAS) datasets, and an initial sample (10%) will undergo a quality control audit requiring no more than 5 discrepancies per 10,000 fields

(0.05%). If this limit is exceeded, the data sample will be expanded to a full (100%) audit for the offending data module. All discrepancies will be documented and corrected, where possible, in the final locked database.

2 INTRODUCTION

This Statistical Analysis Plan (SAP) describes the statistical analysis methods and data presentations to be used in the summary and analysis of Protocol No. 0911010739, Amendment 10, dated 27 June 2013. Related documents are the study protocol and CRF.

From experiences gained from this and other studies of macrobeads containing mouse renal adenocarcinoma (RENCA) cells, it has become apparent that tumor measurements often cannot be obtained from patients with such advanced disease due to a lack of tolerance to imaging contrast. As a result, certain efficacy parameters (such as response rate) described in the protocol have been modified to better fit the patient population. Therefore this SAP supersedes the statistical considerations identified in the protocol.

3 INVESTIGATIONAL PLAN

3.1 Study Objectives

The primary objective of the study is to determine the efficacy of RENCA cell-containing macrobeads in each of two patient populations (Stage IV colorectal carcinoma or pancreatic carcinoma). The secondary objective is to determine the safety and tolerability of implanted macrobeads in each population and in both populations combined. The exploratory objective is to identify mechanisms associated with the antitumor activity of implanted macrobeads, which could include examination of the niches of cancer stem and other cells within the niche bodies of the tumors.

3.2 Study Design

This is an open-label, non-randomized, single-center Phase II trial to evaluate the efficacy, safety and tolerability of RENCA cell-containing macrobeads implanted in Stage IV subjects with colorectal or pancreatic cancer in whom standard and accepted therapy such as chemotherapy, radiation and/or surgery have failed and who have chosen to not pursue other experimental therapies. Patients will be implanted with RENCA macrobeads, which will permanently remain in the peritoneal cavity even if patients discontinue from the study or begin a new therapy (e.g., chemotherapy).

Screening will occur within 28 days prior to implantation. Each eligible subject who signs an Informed Consent Form (ICF) will be considered as "enrolled". Subjects who sign an ICF but who are not implanted will be replaced. A total of 30 subjects (20 with colorectal cancer and 10 with pancreatic cancer) will be implanted. Detailed inclusion and exclusion criteria are given in [Protocol Section 4.3](#).

Subjects will receive up to 4 macrobead implantations, with at least 3 months between each implantation procedure. The primary focus of the trial is to estimate specific clinically important parameters for use in planning subsequent regulatory trials designed to more fully assess efficacy, safety and tolerability. Subjects will undergo formal safety and efficacy assessments for

120 days after their final implantation. After this formal phase of the trial has been completed, subjects will be followed for the duration of their lives.

Data output and analyses will be stratified by cancer type. There are no pre-specified comparisons between the two cancer types.

The study will end 120 days after the last active subject undergoes their last implantation.

3.3 Study Outcomes

3.3.1 Efficacy

The primary efficacy outcome is post-implantation all-cause mortality, where time to death is defined as the time from the first scan showing disease progression after completion of prior treatment (time of origin, T_0) to death from any cause.

Secondary efficacy outcomes are (if feasible):

- Time from first implantation to death.
- Time from disease Stage IV diagnosis to death.
- Changes from baseline based on Magnetic Resonance Imaging (MRI), computerized tomography (CT) or positron emission tomography (PET)-CT scan, and other appropriate imaging techniques (e.g., sonography, bone scans, other x-rays) as indicated, if feasible.
 - In primary and/or secondary tumor size (volume, area) and
 - In state (necrosis, vascularization) on MRI, CT or PET-CT scan, and other appropriate imaging techniques (e.g., sonography, bone scans, other x-rays) as indicated.
- Change from baseline in tumor markers (CEA, CA19-9)
- Changes from baseline in CA125 (as a marker of inflammation)
- Changes from baseline in
 - Clinician Global Clinical Assessment
 - Activities of daily living
 - Symptom rating
 - Quality of life (QCQ-C30)
 - Pain scale
 - ECOG
- Additional exploratory efficacy outcomes may be analyzed if feasible and will be defined in the CSR.

3.3.2 Safety

Safety outcomes will include:

- Reason for study discontinuation (coming off protocol).
- Incidence of adverse events (AEs).
- Changes from baseline in physical examination parameters, including weight, vital signs, and electrocardiogram (ECG).

- Changes from baseline in laboratory parameters (see [Section 11.1.3](#)).
- Changes from baseline in murine antigens skin test.
- Changes from baseline in status of murine leukemia virus as detected by polymerase chain reaction (PCR).

3.3.3 Exploratory

Exploratory outcomes will include presence or absence of circulating tumor cells, examination of pathology specimens (when possible / available) for cancer stem cell niches, and any other analyses of interest as the current state of research in this area evolves.

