3.2.2 Secondary Objectives

1. To determine the safety and tolerability of the implantation of the RENCA cancer-cell-containing macrobeads in advanced pancreatic cancer subjects with respect to:
 - The peritoneum: irritation, inflammation, mechanical effects (over a period of at least 3 months);
 - Other intraperitoneal organs (liver, spleen, large and small intestines, kidney, bladder, omentum, etc.);
 - Local and systemic immune response (T and B cell/cellular, antibody responses);
 - Bacterial, viral zoonotic infection (clinical and hematological examination; PCR DNA analysis for viral DNA; specific viral antibodies);
 - Hypersensitivity reactions to murine antigens.
2. To determine progression, defined as the time from the first implantation until the first occurrence of any of the following events
 - a. Death due to any cause, or
 - b. Progression as defined by the presence of the occurrence of any three of the five following events:
 - i. An increase in the levels of tumor markers (e.g., CEA, CA19-9) of 50% from baseline determinations
 - ii. Radiographic progression including increase in primary or metastatic tumor size/volume; increasing metabolic activity of the presenting tumor or of new metastatic lesions on a PET/CT scan after the administration of radio-labeled fluorodeoxyglucose (FDG); and evidence of new metastatic lesions.

- iii. A decrease in the EORTC QLQ-C30 quality of life scale as compared to baseline of more than 25%;
(Above data will also be analyzed with censorship of deaths to further evaluate progression)
3. Determine overall survival (OS)
4. Circulating tumor cells will also be measured

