4 INVESTIGATIONAL PLAN

4.1 *Description of Overall Study Design and Plan*

This is an open-label clinical trial. The clinical trial will have duration of approximately 12 months and involve a potential total of four macrobead implants, each no less than three months apart.

Each subject will serve as his own control. This means that changes from baseline to various post-treatment time points will be analyzed for some variables (such as tumor markers, for example). The confidence intervals for these changes will be calculated. Of course, it is not planned for the survival analysis.

Seventy-four (74) male and female subjects with advanced pancreatic cancer or metastatic, treatment-resistant colorectal cancer meeting all the above inclusion criteria will be recruited and treated for the study. Baseline measurements will include tumor burden and size, tumor history and pathological diagnosis and grade, global clinical state, activities of daily living, symptom checklist including tumor-related symptoms, a sense-of-well-being scale, routine clinical biochemistry and any appropriate tumor markers as available, and an assessment of cellular and humoral immune status.

The primary tumor histopathology will be reviewed and will be evaluated with special staining to identify, if possible, the presence or absence of cancer stem cells and niche bodies.

The response of each subject to the intraperitoneal implantation of the RENCA agarose-agarose macrobeads will then be measured over the ensuing 3 months (and a 6, 9, and 12 months, if possible) with respect to changes in:

- Primary tumor size
- Size or number of secondary/metastatic tumors
- Tumor marker or relevant biochemical parameters such as liver enzymes, alkaline phosphatase, lactic dehydrogenase
- Cellular or humoral immune status
- Global clinical status or rating
- Performance status (Karnofsky PS and ECOG PS)
- Activities of daily living (ADL) rating
- Symptom rating/severity (including use of pain medications)
- Quality of life scale
- Circulating tumor cells (when possible)

After each successive implant, follow-up will be at Days 14, 30, 60, and 90. Because much of the testing will be objective in terms of quantifiable clinical laboratory and imaging testing, bias on the part of subjects, investigator, and analysts should be minimized.

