4.6 Assessments

The objective of the proposed Phase II study of the RENCA macrobeads is, as stated above, to determine the human clinical efficacy of the cancer macrobeads in advanced pancreatic and colorectal cancer. Responses will be

assessed according to the usual categories of complete or partial response (with specification of percentage), and none/progression (with specification of percentage). Response assessment will be measured in terms of changes in volume of primary tumor and number of metastases as assessed by CT or MRI; tumor marker PSA, as well as the physician global clinical assessment; performance rating scale (Karnofsky or similar); quality of subject life as measured by the EORTC Quality of Life Scale. Alkaline phosphatase and lactic dehydrogenase will also be followed.

Other laboratory determinations to monitor subject response to the implantation of the macrobeads will include detection of inflammatory responses (CBC with differential WBC and platelet count, erythrocyte sedimentation rate, C-reactive protein, amylase, immunological changes, and cytokine production), RT-PCR (polymerase chain reaction) specific to e-MuLV DNA, plasma viremia, and antibodies to normal murine antigens.

A critical and unique addition to the endpoints for assessing efficacy will be, where possible, a careful search for and identification of the niches of cancer stem and other cells within the niche bodies of the tumors the macrobeads are being used to treat. Markers of the niche bodies used to identify them and study their state (numbers, integrity of surround blood vessels, degree of stress) will include HLA, CD44+, CD133+, p27, Ki67, and the Tunel assay for apoptosis. Determination of the presence or absence of circulating tumor cells will also be made. When possible/available, pathology specimens will be examined for cancer stem cell niches.

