5 STUDY CONDUCT

5.1 *Schedule of Assessments*

Clinical procedures, laboratory tests, and other measures to be utilized (and their order and flow) in the trial are indicated in Appendix 2 (section 9.2), and below:

5.1.1 Study Days -28 to -1:

1. Pretreatment evaluations used to determine the subject's study eligibility must be completed within 28 days prior to implantation unless otherwise specified for particular individuals and circumstances
2. Written informed consent must be obtained prior to performing to any study-specific evaluations. Results of all pretreatment evaluations must be reviewed by the Principal Investigator or his/her designee to ensure that all eligibility criteria have been satisfied prior to subject implantation. There will be a complete review of the subject's cancer history and reports of tumor biopsies obtained. A series of clinical tests and procedures are to be performed at different intervals throughout the study.
3. All subjects must undergo the following pretreatment evaluations:
 - Medical history (including an assessment of baseline conditions, global clinical assessment, symptoms rating/severity assessment, quality of life scale [EORTC], pain scale assessment and activity of daily living rating)
 - Physical examination (including neurological examination, height and weight measurements)
 - Recording ECOG Performance Status and Karnofsky Performance Status
 - Vital signs (including temperature, pulse rate, respiration rate and blood pressure)
 - Concomitant medication assessment (including those medications taken within 30-days prior to implantation)
 - Hematology profile (CBC with differential WBC and platelet count)
 - Coagulation profile (PT, PTT and INR)
 - Erythrocyte sedimentation rate
 - Comprehensive chemistry profile (CO₂, sodium, potassium, chloride, creatinine, BUN, glucose, calcium, total protein, albumin, total bilirubin, alkaline phosphatase, AST and ALT), glucose, GGT, LD
 - Urinalysis, and if clinically indicated, a 24-hour urine collection
 - Amylase, lipase
 - Serum direct bilirubin

- Immunoglobulin levels
- Tumor markers: CEA, CA 19-9, CA 125.
- Circulating Tumor Cell levels (if possible)
- Baseline ECG within 28 days of implantation
- PA/lateral chest x-ray (within 28 days of implantation). If chest x-ray results indicate potential thoracic cancer-related abnormalities, then perform a non-contrast chest CT (within 21 days of implantation).

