A critical safety parameter will be the determination of the presence or absence of antibody to murine viruses, including mouse leukemia virus (MuLV), as well as viral titers for murine viruses known to be infective for humans. The published literature and the co-culture experiments carried out in our laboratory do not indicate that MuLV can infect human cells. Furthermore, the RENCA cells used to prepare the cancer macrobead have tested negative for other known murine viruses (Charles River panel of 18 murine viruses). In addition, none of the thirty-one (31) subjects treated to date in the Phase I study have shown any evidence of viral infection associated with the macrobeads. Nonetheless, this protocol includes laboratory and clinical monitoring for any such viral transmission. If there is any laboratory or clinical evidence indicating or suggesting a viral infection with MuLV, all family members having direct physical contact with that subject will also be assessed for the identified murine virus or for any clinical or laboratory evidence of a known or unknown viral infection. Virological monitoring of all staff in contact with the subject will be carried out at that time as well. It should be emphasized again that there has been no evidence of such transmission or infection in the Phase I trial.

5.1.6 Visit 2, Study Day 14 ± 3 days:

A brief examination including the parameters listed below will be performed. Assuming that the wound examination is satisfactory, all sutures/staples will be removed by the surgeon who performed the laparoscopy or appropriate surrogate. In addition, the Investigator will also examine the subject.

The following data will be obtained:

- Vital signs with weight
- Physical examination with brief neurological exam
- CBC with differential WBC, platelet count
- Coagulation profile (PT, PTT and INR)
- Erythrocyte sedimentation rate
- Comprehensive Metabolic Panel with LD, GGT, CRP, direct bilirubin

- Cytokine panel
- CEA, CA 19-9, CA 125
- Circulating Tumor Cell Levels
- Monitoring of adverse events and concomitant medications
- Global clinical assessment
- Quality of life scale
- ECOG and Karnofsky Performance status rating
- Pain scale, if appropriate

5.1.7 Visit 3, Study Day 30 ± 5 days:

The following data will be obtained:

- Vital signs with weight
- Physical examination with brief neurological exam
- CBC with differential WBC, platelet count
- Coagulation profile (PT, PTT and INR)
- Erythrocyte sedimentation rate

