Coagulation Panel ²	X																						
Erythrocyte sedimentation rate	X																						
Comprehensive Metabolic Panel ³	X																						
GGT ⁴	X																						
Amylase ⁵	X																						
Lipase ⁵	X																						
Lactate Dehydrogenase	X																						
C-Reactive Protein	X																						
Bilirubin, Direct	X																						
Hepatitis Panel ⁶	X																						
HIV	X																						
Serum Pregnancy (Qualitative) ⁷	X																						
Immunoglobulin Levels ⁸	X																						
Cytokine Panel ⁹	X																						
Cellular Immune Function ¹⁰	X																						
Ecotropic Murine Leukemia Virus	X																						

	Screening	Visit 1 / Day 0	Visit 2 / Day 14	Visit 3 / Day 30	Visit 4 / Day 60	Visit 5 / Day 90	Visit 6 / Implant 2	Visit 7 / Day 14	Visit 8 / Day 30	Visit 9 / Day 60	Visit 10 / Day 90	Visit 11 / Implant 3	Visit 12 / Day 14	Visit 13 / Day 30	Visit 14 / Day 60	Visit 15 / Day 90	Visit 16 / Implant 4	Visit 17 / Day 14	Visit 18 / Day 30	Visit 19 / Day 60	Visit 20 / Day 90	Visit 21 / Day 120	Follow-Up ¹²
Immunohistochemical & Gene Array Analysis (when indicated)		X					X					X					X						
Murine Allergen Skin Test with positive and negative controls	X					X					X												
Circulating Tumor Cells	X		X	X	X	X		X	X	X	X		X	X	X	X		X	X	X	X	X	
Macrobeads Implantation (8 per kg body wt)		X					X					X					X						
Cefazolin (Prophylaxis – 1 gm)		X					X				X						X						
Chest X-Ray (PA/lateral)	X					X					X						X						
CT Scan Chest (Non-Contrast) ¹¹	X					X					X						X						
MRI of Abdomen ¹¹	X					X					X						X						X
MRI of Pelvis ¹¹	X					X					X						X						X
Tumor Mass Biopsy (where indicated)		X					X										X						X
PET-CT Scan Whole Body	X					X					X						X						X ¹¹
Radionuclide Bone Scan ¹¹																							

¹ Hematology Profile: WBC, RBC, hemoglobin, hematocrit, MCV, MCH, MCHC, RDW, platelets, automated differential WBC

² Coagulation Panel: PT, PTT, INR

³ Comprehensive Metabolic Panel: CO₂, sodium, potassium, chloride, creatinine, BUN, calcium, total protein, albumin, total bilirubin, alkaline phosphatase, AST, ALT, glucose

⁴ GGT: gamma glutamyl-transpeptidase

⁵ Amylase and lipase are done at baseline, then as medically necessary for individual subjects

⁶ Hepatitis Panel: Hepatitis B, C and E

⁷ Serum pregnancy only for females of childbearing potential

⁸ Immunoglobulin Levels: IgA, IgG, IgE and IgM

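### Circulating tumor cells are collected as levels at the post-implant visits, but the only pre-specified outcome is presence or absence; the level and its change from baseline should be pre-specified too.

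*SAP*

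**What the plan says.** **Collection.** Protocol 5.1.1 asks for circulating tumor cell levels at screening, if possible. From 5.1.6 on, the visit lists include "Circulating Tumor Cell Levels" at Days 14, 30, 60 and 90 after each implant. The cells are measured again at Day 120 of the fourth implant (5.1.25). Protocol Appendix 2 marks the same visits.

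**Purpose.** Protocol 4.1 puts the cells, when possible, in its list of measures by which each subject's response is assessed as change. For pancreatic cancer, protocol 3.2.2 has a secondary objective: "Circulating tumor cells will also be measured". It gives no scale.

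**Outcome.** SAP 3.3.3 states "Exploratory outcomes will include presence or absence of circulating tumor cells", and protocol 3.1.3 matches it for colorectal cancer. Protocol 4.6 says "Determination of the presence or absence of circulating tumor cells will also be made". The SAP sentence ends with an open clause: "any other analyses of interest as the current state of research in this area evolves".

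**Planned output.** SAP 10.1.3 covers CEA, CA 19-9, CA125, C-reactive protein, sedimentation rate, cytokines and other laboratory measures, several with individual plots over time. Circulating tumor cells are not among them. SAP section 16 has no listing, table or figure with their name.

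**The concern.** A present/absent outcome registers only subjects who cross the cut-off. As a hypothetical illustration, a fall from 50 cells to 5 and a rise from 5 to 50 both read as no change. Yet change within the subject is what protocol 4.1 lists the cells for, and it is how the SAP treats CEA and CA 19-9.

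SAP section 2 says tumor measurements often cannot be obtained in these patients, which adds some weight to serial blood measures. SAP 3.2 says the trial's main purpose is to estimate parameters for planning later trials. A positivity proportion gives a planner no estimate of the size of change in level. A level analysis added later under the open clause would be chosen after the data are seen, in an open-label single-arm trial.

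**Working it through.** **1. Visits with a measurement.** Four visits after each of four implants, plus Day 120: 4 × 4 + 1 = 17. With screening this makes 18, which matches the 18 marks in the protocol Appendix 2 row. The row in SAP section 4 shows 8 marks in the text available. That table may be damaged by extraction, so it should be checked against the original before anything is read into it.

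**2. Nearest figure in the plan.** No figure is given for circulating tumor cells. Protocol Appendix 3, item 9, gives worst-case precision for a rate, which would apply to a positivity proportion. The half-width is 1.96 × √(0.25/n):
- n = 20: 21.9 points; n = 10: 31.0 points. These reproduce the stated 22 and 31, which belong to the original 20 and 10 subjects.
- n = 34 (74 − 40, colorectal): 16.8 points; n = 40 (pancreatic): 15.5 points.

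This is the precision of a proportion at one visit. It says nothing about change in level.

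**3. Why the binary outcome misses change.** For a Poisson count with rate λ, and a cut at zero (assumed, since the documents state no cut-off), the chance of a negative result is exp(−λ).
- λ falls from 8 to 4: from exp(−8) = 0.03% to exp(−4) = 1.8%. Almost nobody changes category.
- λ falls from 1 to 0.5: from exp(−1) = 37% to exp(−0.5) = 61%. Some do.

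**4. Illustrative size.** All inputs are assumptions: Poisson counts, lognormal between-subject SD 1.2 and within-subject SD 0.4 on the log scale, a true halving from baseline to one follow-up, two-sided 5%. The level is tested by Wilcoxon signed-rank on the difference in log(count+1), and present/absent by exact McNemar. Results for n = 40:

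| Baseline positivity | Level | Present/absent | Difference |
|---|---|---|---|
| 26% | 29% | 13% | 16 points |
| 61% | 73% | 30% | 43 points |
| 94% | 100% | 9% | 91 points |

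At n = 20 (the SAP's colorectal size) the same model gives 44% against 9% at 61% positivity (35 points) and 89% against 2% at 94% (87 points). At n = 10 (the SAP's pancreatic size) the difference at 61% is roughly 15 to 20 points.

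**5. Second model.** Same log-SD of 1.2, within-subject correlation 0.7, a halving, n = 40: 31% against 17% at 30% positivity, 52% against 28% at 50%, 86% against 30% at 80%, and 97% against 9% at 95%. The direction is the same throughout. Among subjects whose count of 2 or more falls by at least half, about 30% stay positive at 30% baseline positivity and about 85% at 95%.

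**6. Caveat on the comparison.** Exact McNemar cannot reach two-sided 5% with fewer than six discordant pairs: 2 × 0.5⁵ = 0.063, while 2 × 0.5⁶ = 0.031. Part of the gap in small samples comes from this discreteness.

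**The case against.** The strongest reply is that the plan does not confine itself to present/absent. SAP 3.3.3 says what outcomes will include and then leaves other analyses open. SAP 3.3.1 lets further exploratory efficacy outcomes be defined in the clinical study report. SAP 11.1.3 sends observed values of all laboratory parameters to a spreadsheet and plans change from baseline for selected ones, and section 16.1 has an "other labs" listing. So a reader who infers that levels are thrown away, or can be analysed only as present or absent, goes beyond the documents. This part of the reply stands. It does not supply a level analysis: neither SAP 11.1.3 nor protocol 5.6 names circulating tumor cells, and keeping a value is not the same as planning its analysis.

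A reader might also infer that most of the information is lost, on the view that metastatic patients are nearly all positive at baseline. The documents give no positivity rate, distribution, assay or cut-off. The loss is moderate at low positivity and severe at high positivity, and nothing here says which applies. Nor is the gain uniformly large: at n = 40 and 26% positivity it is 16 points.

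Power is also an imperfect yardstick. SAP 6.2 and 10.2 make all testing exploratory, and no test of these cells is planned. The figures show relative information and are not an operating characteristic of the trial. Other objective serial markers exist and are summarised on their own scale. The statement in protocol 4.1 that each subject is his own control covers some variables and does not name this one, although the response list in the same section does.

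**Conclusion.** The concern holds as a gap in pre-specification. Levels are collected and listed for assessment of change, but the only outcome defined cannot show change in a subject who stays positive, and no level analysis or named output is planned. That much follows from the text alone.

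The size depends on assumptions about positivity, spread, cut-off and effect. Under those used, the level was more informative in every setting shown above, with a difference at n = 40 of 16 to 91 points of power; differences are smaller in absolute terms at n = 20 and n = 10.

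The consequence is limited. The SAP classes the outcome as exploratory, and no decision, sample size or error rate rests on it. This is a worthwhile improvement and not a threat to the trial's conclusions. The documents do not support saying that the data are discarded or that most of the information is lost.

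**What to change.** In SAP 3.3.3 and 10.1.3, and in protocol 3.1.3:
- Pre-specify the circulating tumor cell level and its change from the value before the first implant, on the log(count+1) scale or by a rank method. Give the median change with a 95% CI and the number sampled at each visit, by cancer type.
- Plot individual profiles, as planned for CEA and CA 19-9.
- Add a listing and a table to SAP section 16.
- State the assay's positivity cut-off and keep present/absent as a supplementary summary.

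At the same time, align the SAP with the pancreatic secondary objective in protocol 3.2.2, and check the SAP section 4 row against protocol Appendix 2.

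The cost is some wording, one more table with its listing and plots, and a rule for zeros. No new data collection is needed.
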